10.2.2. Operational endpoints

Accuracy of serum urate titration will be evaluated relative to the average levels from the week 12 visit onward and relative to the proportion of samples that are within the target range. Inosine dosage associated with accurate titration will be summarized. Urine pH trajectories and the frequency of alkalization will be summarized.

10.2.2.5 Power Calculations

Assuming that 50%, 20%, and 10% of participants in the placebo group are expected to experience an AE or a given type of AE, we will have 80% power to declare a significant treatment-dependent increase in the proportion experiencing an AE if at least 95%, 71%, and 59% of participants in the inosine group are expected to experience an AE, respectively. We will have 80% power to observing at least one instance of any inosine-associated AE with a true probability of occurrence of at least 8%. For tolerability, we will have 80% power to declare inosine tolerable if the true proportion tolerant is at least 71%. Variance component estimates for calculating power for effects of treatment on ALSFRS-R are from a single arm pilot study of 25 participants on inosine for 20 weeks. Based on the follow-up schedule for this trial and assuming a random-slopes model, the estimated effective SD for ALSFRS-R slope per month is 1.4. Given this estimate, we will have 80% power to detect a difference in ALSFRS-R slopes between the inosine and placebo groups of 1.05 units per month. We will have 12% power for a difference in slopes of 0.3 units per month.

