⁴ Screening labs include uric acid, urinalysis and Serum pregnancy test (WOCBP) and will be performed at local institution.

Inosine in ALS

V3.0

7/01/2019

⁵ Uric acid level will be measured just before the first dose (Baseline visit) or just before scheduled morning dose (trough) (Weeks 3, 6, 9, 12, 16, 20) (Quest Diagnostics)

⁶ Urinalysis with sediment (Quest Diagnostics)

⁷ Safety labs include Hematology (CBC with differential), Basic Metabolic Panel, Liver Function Tests and will be performed at local institution.

⁸ Pulmonary Function Testing includes Slow Vital Capacity (SVC)

⁹ Adverse events that occur AFTER signing consent form will be recorded.

¹⁰ App installation and un-installation procedures include a brief survey about phone use

STUDY WORKFLOW

[figure not shown]
Screening Period

On Active Treatment

Washout Period

[figure not shown]
[figure not shown]
~ 60 Screened

15 Subjects on inosine (administered as 500 mg caps; 1 to 6 caps a day; dose titrated to target urate levels of 7 - 8 mg/dL).

15 Subjects on placebo (administered as 500 mg caps; 1 to 6 caps a day; pseudo-titration will be performed to maintain blinding).

21 Days

Subjects who discontinue from the study early will be asked to return to the study site for Final Safety assessments, and will be asked to have a final Follow-Up Telephone Call 28 days (+5 days) after taking their last dose of study drug.

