4 STUDY DESIGN

4.1 Overall Study Design and Plan

During the enrollment period, approximately 60 subjects will be screened at up to three (3) Northeast ALS Consortium (NEALS) Centers in the United States. Approximately 30 of these subjects are expected to be found eligible for study enrollment and will be randomized 2:1 to receive inosine or placebo. Per study protocol, the aim is to elevated serum urate levels only in those subjects whose baseline urate level falls below the predicted median for this population. Approximately 30 subjects will receive inosine or placebo for 20 weeks (administered in the form of 500 mg capsules, 1 to 6 capsules a day for a total daily dose of up to 3 gm). The dose of inosine will be titrated to target urate levels of 7-8 mg/dL based on urate level measurement that will occur at the Week 3, Week 6, Week 9, Week 12 and Week 16 visits. Clinic visits will occur at Screening, Baseline, Week 12, Week 20 and Unscheduled Safety Visits. Telephone visits and remote serum urate testing will occur at Week 3, Week 6, Week 9 and Week 16. There will be a window of ± 3 days for each visit. The Screening Visit must be completed within 21 days of the Baseline Visit. All visit windows are consecutive calendar days and are calculated from the day the participant starts study treatment (Day 0, the day of the Baseline Visit).

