10.2.2.2 Tolerability

Tolerance will be defined as completion of the 20-week study without permanently discontinuing study drug or suspending study drug for greater than 28 days. Tolerability of inosine vs. placebo will be based on the proportion determined tolerant at week 20 and compared by Fisher's exact test from the AT sample. Serum urate elevation via oral inosine as titrated in this study will be judged tolerable if the lower one-sided 95% confidence bound on the proportion tolerant is greater than 50%.

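### The tolerability rule does not have 80% power at a true rate of 71%: with 20 inosine subjects it has 46% (exact bound) or 65% (approximate bound)

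*Combined protocol and SAP*

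**What the plan says.** Tolerability is one of the two primary outcomes (section 3.2). Section 10.2.2.2 defines it: "Tolerance will be defined as completion of the 20-week study without permanently discontinuing study drug or suspending study drug for greater than 28 days". The same section sets the criterion: urate elevation with inosine "will be judged tolerable if the lower one-sided 95% confidence bound on the proportion tolerant is greater than 50"%. It does not say how the bound is calculated.

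Section 10.2.2.5 gives the power: "For tolerability, we will have 80% power to declare inosine tolerable if the true proportion tolerant is at least 71"%. It does not state the number of inosine subjects. Section 4.1 supplies that: "Approximately 30 of these subjects are expected to be found eligible for study enrollment and will be randomized 2:1 to receive inosine or placebo", which gives 20 on inosine and 10 on placebo. The Study Workflow in the Protocol Summary disagrees; it shows "15 Subjects on inosine" and the same number on placebo.

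**The concern.** With 20 subjects, a lower 95% bound above 50% needs an observed proportion of at least 70% or 75%, depending on the method. A true rate of 71% sits at about that level, so the rule would pass roughly half to two thirds of the time. A claim of 80% power there is not credible on its face.

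This matters because tolerability is the only primary outcome with a stated success threshold. A reader of 10.2.2.5 would believe that a drug tolerated by 71% of patients has a one-in-five chance of missing the criterion. The actual chance is 54% with the exact bound or 35% with an approximate one. The unnamed method adds a second problem: 14 of 20 passes under Wilson and fails under Clopper-Pearson, so the primary conclusion could turn on a choice made after the data are seen.

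**Working it through.** **Inputs**
- Rule: lower one-sided 95% bound above 0.50 (10.2.2.2).
- Claim: 80% power at a true rate of 0.71 (10.2.2.5).
- Inosine arm: 30 × 2/3 = 20 (4.1).
- Dropout: failure to complete already counts as not tolerant (10.2.2.2) and withdrawals are not replaced (5.3), so no further adjustment applies.

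**Is 20 the size used in the power section?** The other figures in 10.2.2.5 say yes.
- For "at least one instance of any inosine-associated AE with a true probability of occurrence of at least 8"%, the chance of seeing one or more events is 1 − 0.92^20 = 81.1%. With 15 subjects it is 1 − 0.92^15 = 71.4%.
- One-sided Fisher power for the three AE scenarios (50% v 95%, 20% v 71%, 10% v 59%) is 79.7%, 80.1% and 79.7% with 20 v 10. With 15 v 15 it is 84.3%, 82.4% and 83.1%.

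The tolerability sentence is the one that does not fit.

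**Method.** For each type of bound, find the smallest count r out of 20 whose lower bound exceeds 0.50. Then power = P(X ≥ r), with X binomial (20, 0.71), and one-sided error = P(X ≥ r) with X binomial (20, 0.50).

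**Reproducing the stated figure.** P(X ≥ 13 | 0.71) = 80.2%, and power reaches 80% at a true rate of 70.9%. So the plan's pair of numbers corresponds to a cut-off of 13 of 20. The table shows that this cut-off does not meet the rule.

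| Tolerant of 20 | Exact bound | Wilson | Wald | Jeffreys | Error at 50% | Power at 71% | True rate for 80% power |
|---|---|---|---|---|---|---|---|
| 13 | 0.442 | 0.467 | 0.475 | 0.467 | 13.2% | 80.2% | 70.9% |
| 14 | 0.492 | 0.516 | 0.531 | 0.518 | 5.8% | 64.6% | 75.5% |
| 15 | 0.544 | 0.568 | 0.591 | 0.571 | 2.1% | 45.5% | 79.9% |

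The exact bound first exceeds 0.50 at 15 of 20. The other three do so at 14 of 20. None does so at 13. An approximate one-sided **90%** bound would pass 13 of 20 (Wilson 0.507, Wald 0.513). That may be how the figure arose, but the documents do not confirm it.

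**Normal-approximation power** for n = 20, one-sided 5%: 60% (null variance), 66% (alternative variance), 62% (arcsine), 50% (continuity-corrected). None is near 80%.

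**Other arm sizes**
- n = 15, as in the Study Workflow: 32.7% (exact, at least 12) or 55.0% (approximate, at least 11).
- All 30 subjects pooled: at least 20 of 30 by every method, power about 77%. A normal approximation with the alternative variance gives 81.3% at this size, but the rule concerns inosine recipients.
- From 15 to 25 inosine subjects, no Clopper-Pearson, Wilson, Wald or Jeffreys bound reaches 80%. Because counts are discrete, approximate bounds just reach it at isolated larger sizes: 17 of 26 with Wald (bound 0.654 − 1.645 × √(0.654 × 0.346/26) = 0.5004, power 80.4%) and 19 of 29 (power 80.6%). Neither is an inosine arm that the plan describes.

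**The case against.** The strongest reply is that the sentence does no work. The rule in 10.2.2.2 is what will be applied to the data, and correcting the power statement changes no endpoint, threshold, analysis or patient count. Nor do the documents say that about 30 subjects were chosen to meet this power, or that 71% is the expected rate. Section 2.3.1 reports that 95% of participants tolerated treatment at 6 months in the earlier Parkinson's disease trial. If tolerance here were that high, the criterion would almost certainly be met: exact-bound power with 20 subjects is 80.4%, 93.3%, 98.9% and 99.97% at true rates of 80%, 85%, 90% and 95%. The plan also attaches no programme decision to the rule, and it includes a Fisher comparison with placebo.

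Much of this stands. The error does not bias the estimate, and it may have little effect if tolerance is high. But the 95% comes from another disease. In ALS, progression or death can also prevent completion, so rates of 71% to 80% cannot be ruled out. The reply does not defend the number itself, and it leaves the missing interval method untouched. That omission does affect the analysis, because 14 of 20 is a pass or a fail depending on the method.

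It is also fair that 20 is inferred from an approximate total and that the Study Workflow shows 15. The other power figures support 20, and 15 makes the shortfall larger.

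**Conclusion.** The stated 80% power at 71% is wrong. With 20 inosine subjects and the written rule, power is 45.5% (Clopper-Pearson, at least 15 of 20) or 64.6% (Wald, Wilson or Jeffreys, at least 14 of 20). That is a shortfall of 34.5 or 15.4 percentage points. The true rate needed for 80% power is 79.9% or 75.5%. The figure in the plan fits a 13 of 20 cut-off, which breaches the rule and would carry a 13.2% one-sided error at a true rate of 50%.

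This rests on an inosine arm of 20 (30 subjects at 2:1) and on independent binomial outcomes. The range from 45.5% to 64.6% reflects only the unnamed interval method. Because this is the stated power of a primary outcome, it must be corrected.

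**What to change.** 1. In 10.2.2.2, name the interval and give the cut-off as a count.
2. In 10.2.2.5, state the number of inosine subjects and replace the tolerability sentence. With the exact bound: *With 20 inosine subjects and a Clopper-Pearson lower one-sided 95% bound, inosine is declared tolerable if at least 15 of 20 are tolerant; power is 80% if the true proportion tolerant is at least 80%.* If a Wilson bound is intended, state at least 14 of 20, 80% power at about 75.5%, and an actual one-sided error of 5.8%, which is above the nominal 5%.
3. Make the arm sizes in the Study Workflow agree with section 4.1, and add the number tolerant that is required if the as-treated inosine group is not exactly 20.

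The cost is two or three sentences and a less favourable stated figure. It needs no extra subjects and no change in procedures, and it should be done before unblinding. If the sponsor does want 80% power at 71% with an exact bound, about 35 inosine subjects would be needed (at least 23 of 35, power 81.1%), which is 15 more than planned in that arm.

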5 SELECTION AND WITHDRAWAL OF STUDY POPULATION

5.1 Number of Study Subjects

Approximately 60 subjects will be consented for the study. Any subject who signs consent will be considered enrolled in the study. Screening study procedures will begin after informed consent.

We expect a 50% screen fail rate based on our goal of elevating serum urate levels only in those subjects whose serum urate level falls below the population median. This subpopulation is at greater risk of faster disease progression and can also accommodate an increase in serum urate to higher, but still normal levels, which are known to be associated with slower disease progression^{21, 31, 35}.

Thirty (30) subjects will receive inosine or placebo for 20 weeks per study protocol and will be followed up to Week 24.

If a subject fails screening, at a minimum, the following information will be captured and entered in the data capture system: inclusion/exclusion criteria, demographics, screening lab results, reason for screen failure.

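### The ALSFRS-R power statement does not follow from its own SD: with SD 1.4 and 30 subjects, 80% power needs a slope difference of about 1.4 to 1.6 units/month, not 1.05

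*Combined protocol and SAP*

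**What the plan says.** Section 10.2.2.5 takes variance components from a single-arm pilot of 25 participants. Using this trial's follow-up schedule and a random-slopes model, it reports that "the estimated effective SD for ALSFRS-R slope per month is 1.4". From that value it concludes that "we will have 80% power to detect a difference in ALSFRS-R slopes between the inosine and placebo groups of 1.05 units per month", and adds: "We will have 12% power for a difference in slopes of 0.3 units per month".

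The other inputs are elsewhere:

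- **Test:** section 10.2.2.3 sets two-tailed tests at 0.05 for efficacy.
- **Number treated:** section 5.1 says "Thirty (30) subjects will receive inosine or placebo for 20 weeks per study protocol".
- **Allocation:** section 4.1 says subjects "will be randomized 2:1 to receive inosine or placebo", that is 20 and 10. The Study Workflow in the Protocol Summary shows 15 on inosine and "15 Subjects on placebo (administered as 500 mg caps".

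The same power paragraph also gives adverse-event figures. For placebo rates of 50%, 20% and 10%, there is 80% power "if at least 95%, 71%, and 59% of participants in the inosine group" have an event. There is also 80% power to see "at least one instance of any inosine-associated AE with a true probability of occurrence of at least 8" percent.

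**The concern.** The paragraph supplies an SD and derives a detectable difference from it. The design supplies everything else needed to check that step, and the step fails. A difference of 1.05 is only 0.75 of the stated SD (1.05/1.4), which is a small standardized effect to detect with 80% power in 30 subjects.

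Section 10.2.1 plans to use the ITT sample to estimate efficacy for phase 3. A reader relying on the power section would think the trial would probably detect a 1.05 units/month effect, and could over-read a null ALSFRS-R result as evidence against an effect of that size.

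**Working it through.** **Inputs.** SD 1.4 (10.2.2.5); two-sided alpha 0.05 (10.2.2.3); N = 30 (5.1); allocation 20:10 (4.1) or 15:15 (Study Workflow). The power section states no dropout allowance.

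**Formulas.** SE = SD × √(1/n₁ + 1/n₂). Detectable difference at 80% power (normal) = SE × (1.960 + 0.842) = 2.802 × SE. Power at difference d (normal, upper tail) = Φ(d/SE − 1.960). The t versions use the noncentral t with 28 df.

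**Step 1: try to reproduce 1.05 and 12%.**

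- 20:10: SE = 1.4 × √(1/20 + 1/10) = 0.542; detectable difference 2.802 × 0.542 = 1.52.
- 15:15: SE = 1.4 × √(1/15 + 1/15) = 0.511; detectable difference 2.802 × 0.511 = 1.43.

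| | Stated | 20:10 normal / t | 15:15 normal / t |
|---|---|---|---|
| Detectable difference, 80% power | 1.05 | 1.519 / 1.574 | 1.432 / 1.484 |
| Power at 1.05 | 80% | 49.1% / 46.4% | 53.7% / 50.9% |
| Power at 0.3 (both tails) | 12% | 8.6% / 8.3% | 9.0% / 8.8% |

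Neither allocation reproduces the stated figures. A one-sided 0.05 normal test at 20:10 would still need 1.35, with about 61% power at 1.05. Reading 1.4 as a variance gives 1.28-1.33 at 20:10 and 1.21-1.25 at 15:15.

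**Step 2: what the stated figures imply.** 80% power at 1.05 requires SE = 1.05/2.802 = 0.375. At that SE, power at 0.3 is Φ(0.3/0.375 − 1.960) ≈ 12.3%, or 12.6% counting both tails. The two stated points therefore agree with each other and share one SE, about 0.375. Moving from 0.542 to 0.375 is a variance reduction of 1 − (0.375/0.542)² ≈ 52%, far beyond rounding. It would take one of:

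- at SD 1.4, 56 subjects (normal) to 58 (t) at 1:1, or 63 to 65 at 2:1;
- at 20:10, an SD of 0.97 (normal) or 0.93 (t);
- at 15:15, an SD of 1.03 (normal) or 0.99 (t).

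**Step 3: which per-arm numbers the paragraph uses.** The one-tailed Fisher exact test (10.2.2.1) gives the inosine rate needed for 80% power. The single-event rate is 1 − 0.2^(1/n), with n the number on inosine.

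| | Stated | 20:10 | 15:15 |
|---|---|---|---|
| Placebo 50% | 95% | 95.1% | 93.7% |
| Placebo 20% | 71% | 71.0% | 69.6% |
| Placebo 10% | 59% | 59.1% | 57.0% |
| At least one event | 8% | 7.7% | 10.2% |

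The adverse-event figures use 20 and 10. The ALSFRS-R figures do not fit that base.

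**The case against.** The best defence is that the effective SD is never defined. If 1.4 were the SD of the difference between two subjects' slopes, the per-subject SD would be 1.4/√2 = 0.99. A t test at 15:15 then gives a detectable difference of 1.049, 80.1% power at 1.05 and 12.6% at 0.3, which is close to what is stated. On that reading the fault is one of labelling, and the trial's power at 1.05 is not about half.

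This makes a mislabelled SD a live explanation, but it does not clear the text. The plan calls 1.4 the SD of the slope. The match needs 15:15, against the 2:1 randomization and the adverse-event figures beside it; at 20:10 the same reading gives 75% (t) to 78% (normal) at 1.05. The SD would still need correcting.

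Nor can repeated measures explain the gap: the plan says 1.4 already reflects the follow-up schedule and the random-slopes model, so that gain cannot be counted twice.

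It is also fair to say that little hangs on this for the trial's main purpose. A treatment effect on ALSFRS-R is not among the outcomes listed in section 3.2, nothing shows the trial was sized on it, and the plan already admits low power at 0.3. Phase 3 planning would rest mainly on the observed estimate and its interval. That limits the weight of the point; it does not make the stated power correct.

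**Conclusion.** The concern holds. As written, the SD of 1.4, the 30 subjects and the detectable difference of 1.05 are mutually inconsistent under either allocation in the documents. Taking 1.4 as the per-subject slope SD, which is what the text says, the true detectable difference is about 36% to 50% larger than stated (1.43/1.05 to 1.57/1.05). The chance of detecting 1.05 is about half, rather than 80%.

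The inconsistency is certain. The figure of about half is conditional on 1.4 being correct and per subject, and the documents do not show which input is wrong. These calculations assume complete follow-up; dropout would lower power further, since section 5.3 does not replace withdrawals.

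A lesser point: the power is stated for a slope under a random-slopes model, while section 10.2.2.3 plans a visit-by-visit generalized least squares model and names no contrast to which that power applies. This should be fixed, but it does not touch the primary safety and tolerability conclusions.

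**What to change.** In section 10.2.2.5, define the effective SD, state the number per arm, and reconcile the 2:1 randomization in section 4.1 with the 15 and 15 in the Study Workflow. Then restate both power points:

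- **If SD 1.4 and 20:10 stand:** *80% power for a slope difference of 1.57 units/month; about 46% for 1.05 and about 8% for 0.3.*
- **If SD 1.4 and 15:15 stand:** *80% power for 1.48 units/month; about 51% for 1.05 and about 9% for 0.3.*
- **If 1.05 at 20:10 was intended:** correct the SD to about 0.93-0.97 and show how it follows from the pilot variance components. If 1.4 was meant as the SD of a difference, say so, give the per-subject value and recompute at the actual allocation.

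Add one sentence to section 10.2.2.3 naming the contrast to which the power applies, for example a linear contrast of the visit effects, and the visits that enter it. The model need not change.

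The cost is wording only, with no extra patients. Unless the SD was the error, the stated detectable effect becomes less favorable.

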11 DATA COLLECTION

11.1 Role of Data Management

Data Management (DM) is responsible for the development, execution and supervision of plans, policies, programs, and practices that control, protect, deliver, and enhance the value of data and information assets.

All data will be managed in compliance with applicable Sponsor (or their designee) policies and regulatory requirements. Site personnel will collect, transcribe, correct, and transmit the data onto source documents, Case Report Forms (CRFs), and/or other forms used to report, track and record clinical research data. Clinical sites will be monitored to ensure compliance with data management requirements and Good Clinical Practices. DM is responsible for developing, testing, and managing clinical data management activities.

11.1.1 Data Entry and Checks

The site personnel are instructed to enter information into the Electronic Data Capture (EDC) System within 5 days of a visit. Please Note: Serious Adverse Events (SAEs) must be reported to the Coordination Center within 24 hours of the site learning of the SAE. Data collection is the responsibility of the staff at the site under the supervision of the Site Investigator (SI). During the study, the SI must maintain complete and accurate documentation for the study.

The EDC includes password protection. An edit checking and data clarification process will be put in place to ensure accuracy and completeness of the database. Logic and range checks as well as more sophisticated rules may be built into the eCRFs to provide immediate error checking of the data entered. The system has the capability to automatically create electronic queries for forms that contain data that are out of range, out of window, missing or not calculated correctly. The site will only have access to the queries concerning their subjects.

11.1.2 Data Lock Process

The application will have the ability to lock the database to prevent any modification of data once the study is closed. Once this option is activated, every user will have Read-Only access to the data. The database can only be locked after each Site Investigator (SI) has signed off on their subjects and all queries have been resolved.

